4.6.2 Coding of medications

Medications will be presented in TLF as recorded in CRF. Any coding will be used upon request.

4.7 Handling of Missing Data

Handling of missing data, if applicable, is discussed in the relevant sub-sections of Section 5 (STATISTICAL ANALYSIS: DEFINITIONS, DERIVATIONS, CALCULATIONS AND METHODOLOGY).

4.8 Multiple testing

Not applicable in this study.

	Form	Form No.	1M-DMST-011-01-A1
	Statistical Analysis Plan	Page	Page 13 of 69
		Effective Date	07/05/2018

5. STATISTICAL ANALYSIS: DEFINITIONS, DERIVATIONS, CALCULATIONS AND METHODOLOGY

5.1 Baseline Characteristics

5.1.1 Disposition of Subjects

Collected Variables:

- Treatment group assigned (categories: treatment 1/treatment 2) [CRF – Visit 2]
- Has the subject completed the study (yes, no) [CRF - EOS]
- Primary reason for the premature termination (free text) [CRF - EOS]
- Date of informed consent [CRF – Visit 1]
- Is the subject eligible for entering the study (yes, no) [CRF – Visit 1]
- Inclusion/exclusion criteria (yes, no) [CRF – Visit 1]
- Was the investigational product taken correctly? (yes, no) [CRF – Visit 3, 4, 5]

Derived Variables:

- whether the subject belongs to the :
 - safety set (subjects must have signed the informed consent and they must have taken at least one dose i.e. the answer to the question "Was the investigational product taken correctly" must be "yes" at least once)
 - ITT set (subjects must have been randomized)
 - PP set (subjects must have been randomized and they do not have major deviations)

Imputations for missing values:

If the date of last intake of study medication is not available, due to premature termination or other reasons, date of last investigational product intake (collected in the end of study form of the CRF) will be imputed.

Analysis Sets to be used for:	Tables	Table1: All subjects
	Listings	Tables 2,3, 4: ITT analysis set Listing 1: All subjects Listings 2, 3, 4: ITT analysis set
	Figures	Figure 1: All subjects Figure 2: ITT analysis set

Subject disposition will be summarized by treatment group as follows:

Table 1. Number of Subjects and Subjects Disposition (Total set)	Total number of subjects screened, randomized and number of subjects in analysis sets will be presented by treatment group. The percentage of subjects will be calculated relative to the number of all randomized subjects.
---	---

Table 2. Reasons for premature study termination (All Randomized Subjects)	For study termination and for premature discontinuation reason, a default frequency tabulation will be provided. The percentage of subjects will be calculated relative to the number of subjects who were randomized.
---	---

Table 3. Analysis Sets (All Randomized Subjects)	Subject analyses set status will be summarized for each treatment group, together with the reason(s) for exclusion from the Safety, ITT and PP
---	--

	Form	Form No.	1M-DMST-011-01-A1
	Statistical Analysis Plan	Page	Page 14 of 69
		Effective Date	07/05/2018

analysis sets. Percentages will be calculated relative to the number of subjects who were randomized.

Table 4. Study Status by Visit (All Randomized Subjects)	Study Status by visit identifying number of subjects who continue the study will be presented.
---	--

Subjects data listings will include:

Listing 1. Subjects Who Prematurely Terminated the Study Prior to Randomization	A listing of subjects who prematurely discontinued their participation in the study prior to randomization.
Listing 2. Randomized Subjects Who Prematurely Terminated the Study	A listing of subjects who discontinued participation after randomization.
Listing 3. Visit Dates and Informed Consent Dates	Listing of visit dates and informed consent dates
Listing 4. Analysis Sets	Inclusion/Exclusion from each analysis sets together with the reason(s) for exclusion will be presented. This listing will include all possible reasons for exclusion per subject.

In addition to the tables and listings described above, two figures will present subjects disposition in the form of a flowchart:

Figure 1. Flow Chart of Subjects Disposition	The number of subjects who provided written informed consent, were randomized and the number of subjects per treatment group who completed the study or prematurely discontinued participation in the study will be presented in the form of a flowchart.
Figure 2. Flow Chart of Analysis Sets	The number of subjects considered valid for the Safety, ITT, and PP analyses set per treatment group will be presented in the form of a flowchart.

5.1.2 Demographic and Other Baseline Characteristics

Collected Variables:

- Age (years) [CRF – Visit 1]
- Gender (male, female) [CRF – Visit 1]
- Ethnic group (caucasian, black, asian, other) [CRF – Visit 1]
- Height (cm) [CRF – Visit 1]
- Weight (kg) [CRF – Visit 1]
- BMI (kg/m²) [CRF – Visit 1]

Derived Variables: Not applicable

Imputations for missing values: No imputation of missing data will be performed

Analysis Sets to be used for:	Tables	Safety analysis set
	Listings	All subjects
	Figures	Not applicable

	Form	Form No.	1M-DMST-011-01-A1
	Statistical Analysis Plan	Page	Page 15 of 69
	Effective Date	07/05/2018	

Demography will be summarized by treatment group as follows:

Table 5. Demographics (Safety set) Default descriptive statistics for age, height, weight and BMI will be presented. Frequency tabulations for sex, ethnicity will be presented.

Subject data listings will include:

Listing 5. Demographics

5.1.3 Protocol Violations

Protocol violations are major deviations from the procedures outlined in the protocol like for example missed evaluations, incorrect timing of evaluations, non-compliance with study medications and intake of medications not allowed or any non-adherence to the protocol that impacts subject's rights, safety or welfare.

Protocol violations are defined as any deviations that may affect the efficacy outcome or the treatment of the subjects. All potential protocol violations will be discussed and reviewed on a case-by-case basis. A decision will be made as to the effect of the possible violations to determine if it is considered major or minor. The status, major or minor, of each potential protocol violation will be tabulated. A subject may have one or more major protocol violations resulting in the exclusion of that subject from the per protocol analysis set.

Collected Variables: Not applicable

Derived Variables:

- protocol violation category
- type of violation (descriptive free text)
- details of violation (descriptive free text)

Imputations for missing values: Not applicable

Analysis Sets to be used for:	Tables	ITT analysis set
	Listings	ITT analysis set
	Figures	Not applicable

Protocol violations will be summarized by treatment group as follows:

Table 8. Major/Minor Protocol Violations (ITT set) The number of all subjects with at least one major or minor protocol violation, will be presented by treatment group. For all categories of major and minor protocol violations, default frequency tabulation will be presented. Subjects may have more than one major/minor protocol violation.

Subjects data listings will include:

Listing 6. Minor and Major Protocol Violations A by-subject listing of all subjects with their minor and major protocol violations will be presented.

	Form	Form No.	1M-DMST-011-01-A1
	Statistical Analysis Plan	Page	Page 16 of 69
		Effective Date	07/05/2018

5.1.4 Compliance to Study Treatment and Procedures

Collected Variables

Compliance to the treatment:

- Was the investigational product delivered to the subject? [CRF - Visit 2] (yes/no)
- Was the investigational product taken correctly? [CRF - Visit 3, 4, 5] (yes/no)

Compliance to the study procedures:

- Was the subject fasting for at least 10 hours before IP intake? [CRF - Visit 1] (yes/no)
- Was the investigational device taken by the subject? [CRF - Visit 1] (yes/no)
- Was the blood sampling taken? [CRF - Visit 1, 2, 3, 4, 5] (yes/no)
- Was the V1-V2 DIARY given to the subject? [CRF - Visit 1] (yes/no)
- Was the V1-V2 DIARY checked and retrieved from subject? [CRF - Visit 2] (yes/no)
- Was the V2-V5 given to the subject? [CRF - Visit 2] (yes/no)
- Was the V2-V5 given back to the subject? [CRF - Visit 3, 4] (yes/no)
- Was the V2-V5 DIARY checked? [CRF - Visit 3, 4, 5] (yes/no)
- Was the investigational product retrieved from subject? [CRF - Visit 5] (yes/no)
- Was the V2-V5 retrieved from subject? [CRF - Visit 5] (yes/no)

Derived Variables: Not applicable

Imputations for missing values: Not applicable

Analysis Sets to be used for:	Tables	Safety analysis set
	Listings	Safety analysis set
	Figures	Not applicable

Compliance will be summarized as follows:

Table 6. Compliance to Investigational Product (Safety set)

Compliance to the treatment will be presented by treatment group using default frequency statistics. The percentage of subjects will be calculated relative to the total number of subjects in Safety analysis set. Subjects with missing data will be presented as part of a "Missing" category.

Table 7. Compliance to The Study Procedures (Safety set)

Compliance to the study procedures will be presented by treatment group using default frequency statistics. The percentage of subjects will be calculated relative to the total number of subjects in Safety analysis set. Subjects with missing data will be presented as part of a "Missing" category.

Compliance variables will be presented in subjects data listings as follows:

Listing 7. Treatment Compliance

Treatment compliance data from CRF will be presented as a subject data listing.

Listing 8. Compliance to study procedures [1]

Compliance to study procedures will be presented as a subject data listing.

Listing 9. Compliance to study procedures [2]

	Form	Form No.	1M-DMST-011-01-A1
	Statistical Analysis Plan	Page	Page 17 of 69
		Effective Date	07/05/2018

Inclusion/Exclusion criteria

Collected Variables:

The study specific Inclusion/Exclusion Criteria are presented in Section 8.2 and 8.3 of the *Study Protocol Version Final – March 03, 2018*. For those criteria, as appropriate, a response of “Yes/No” is to be obtained at the screening visit and checked prior to allocated to treatment, at Visit 2.

Derived Variables: Not applicable

Imputations for missing values: Not applicable

Analysis Sets to be used for:	Tables	Not applicable
	Listings	All subjects
	Figures	Not applicable

If a subject fulfills all Inclusion/Exclusion criteria its eligibility will be considered as “Yes”. The response per subject to the study specific Inclusion/Exclusion Criteria, will be presented as a subject data listing as follows:

Listing 14. Inclusion Criteria	Listing of all Inclusion Criteria including the response as either “Yes” or “No” for the eligibility of all subjects.
Listing 15. Exclusion Criteria	Listing of all Exclusion Criteria including the response as either “Yes” or “No” for the eligibility of all subjects.

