9 TREATMENTS

9.1 General

	Study Title	Bioavailability Study of COQUN ORAL FORMULATION (CoQ10) administered in Healthy Adults (CoQ10-01)		
	Study ID	VF-BAQ10/2018	Sponsor:	VISUFARMA SpA
	Date	March 03, 2018	Vers.	Final

The sponsor will provide the investigational site with adequate supplies of the IP. The IP will be produced, packed, and labeled according to national drug laws and GMP. IP shipped to the investigational site will be documented on an appropriate shipment form.

The IP administered to the subjects will be documented on a drug accountability form and in the CRF.

Storage conditions as specified on the drug labels shall apply; the IP shall be kept at temperatures below 25°C, in a dry and cool place and out of reach of children.

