9.7 Drug Accountability and Compliance

The site will be provided with IP shipment and accountability forms to maintain accurate written documentation of all IP transfer processes between the sponsor, the investigator, and the subject. The IP shipment form will be used to document when and the IP quantity delivered to the study site. The accountability form will be used to document when and how much IP is dispensed to the subject. The investigator will document the IP administration to subjects in the source documents.

	Study Title	Bioavailability Study of COQUN ORAL FORMULATION (CoQ10) administered in Healthy Adults (CoQ10-01)		
	Study ID	VF-BAQ10/2018	Sponsor:	VISUFARMA SpA
	Date	March 03, 2018	Vers.	Final

The accountability form must show how much of the IP was used and unused at the end of the study. The monitor will collect the remaining IP, the packages, and the corresponding documentation forms after study completion. The used and unused amount of the IP will be assessed by the monitor by counting. All remaining IP and packages will be returned to the sponsor at the end of the study.

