10.3 Study Schedule

Healthy volunteer subjects who meet the inclusion/exclusion criteria at screening will start the IP administration as follows:

1. a *single-dose* phase; 24 adult healthy subjects will be given a dose of 100 mg of COQUN ORAL FORMULATION and plasma coenzyme Q10 will be measured over the next 12 hours: at 1, 2, 4, 8 and 12 hours after intake. Pharmacokinetic properties including area under the curve (AUC), maximum plasma concentration (Cmax), time to maximum plasma concentration (Tmax) and elimination half-life (t 1/2) will be measured.

2. a *wash-out period* of 1 week

3. a *multidose-dose* phase; 12 adult healthy subjects will be given OD 100mg of COQUN ORAL FORMULATION, after dinner (group A), while the other group of 12 adult healthy subjects will be given BID a dose of 100 mg of COQUN ORAL FORMULATION, after lunch and after dinner (group B); plasma coenzyme Q10 will be measured over the next 4 weeks. Pharmacokinetic properties including area under the curve (AUC), maximum plasma concentration (Cmax), time to maximum plasma concentration (Tmax) and elimination half-life (t 1/2) will be measured.

Subjects will be requested to fill in a short diary in the multidose phase, on a daily basis, for confirming the product correct intake, and informing on any experienced adverse event and eventual medication taken for its solving.

Subjects will have to fast the night before enrolment, for at least 10 hours, then should be seen for all visits on the designated day.

Subjects will be requested to fill in a short diary in the multidose phase, on a daily basis, for confirming the product correct intake, and informing on any experienced adverse event and eventual medication taken for its solving.

Safety assessments will include physical examinations, ECGs, vital signs, standard clinical laboratory evaluations and adverse event (AE) monitoring.

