5.2.2.1 Adverse Events

Collected Variables:

- Event, i.e. diagnosis or signs/symptoms (text) [CRF – Cumulative adverse event form]
- The start and stop date of the event [CRF – Cumulative adverse event form]
- Outcome of event (categories: recovered/resolved, recovered/resolved with residual effects, recovering/resolving, not recovered/ not resolved, fatal, unknown) [CRF – Cumulative adverse event form]
- Severity (categories: mild, moderate, severe, life threatening or disabling) [CRF – Cumulative adverse event form]
- Treatment (categories: none, specific drug treatment, specific non drug treatment) [CRF – Cumulative adverse event form]
- Relationship with study device (categories: definitive, probable, possible, unlikely, none) [CRF – Cumulative adverse event form]
- Action taken with study device (categories: none, dose reduction temporarily, dose reduced, discontinued temporarily, discontinued) [CRF – Cumulative adverse event form]
- Pattern (categories: every study drug administration, intermittent, continuous, other) [CRF – Cumulative adverse event form]
- Seriousness (yes, no) [CRF – Cumulative adverse event form]

Derived Variables:

- Adverse Events (AEs): an adverse event is any untoward medical occurrence in a subject or clinical study subject administered a pharmaceutical product and which does not necessarily have a causal relationship with this treatment. An AE can therefore be any unfavourable and unintended sign, symptom, or disease temporarily associated with the use of a medicinal product, whether or not considered related to the medicinal product. The definition covers the entire study period, independent of whether IP was administered or not.
- Serious adverse event (SAEs): Any untoward medical occurrence or response to a medicinal product that at any dose: results in death, is life threatening, results in in-subject hospitalization or prolongation of existing hospitalization, results in a persistent or significant disability/incapacity, is a congenital anomaly/birth defect or, important AEs that are not immediately life-threatening or do not result in death or hospitalization but may jeopardize the subject or may require intervention to prevent one of the other outcomes listed.

	Form	Form No.	1M-DMST-011-01-A1
	Statistical Analysis Plan	Page	Page 25 of 69
		Effective Date	07/05/2018

In the analysis serious adverse events will be identified by the variables "Seriousness" (yes, no).

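### No planned table or listing shows how much product each arm took: multidose compliance is an undefined yes/no at three visits, although capsules are counted and a daily diary is kept

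*SAP*

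**What the plan says.** SAP 5.1.4 collects two treatment-compliance items: whether product was delivered at V2, and "Was the investigational product taken correctly? [CRF - Visit 3, 4, 5] (yes/no"). It then states "Derived Variables: Not applicable". For Table 6, "Compliance to the treatment will be presented by treatment group using default frequency statistics". The templates for Table 6 and Listing 7 hold only these answers. The remaining items in 5.1.4 ask whether procedures were done: fasting, sampling, diary handed out, checked or retrieved, product retrieved.

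The protocol asks for more than this:

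- Protocol 9.1: "The IP administered to the subjects will be documented on a drug accountability form and in the CRF".
- Protocol 9.7: "The accountability form must show how much of the IP was used and unused at the end of the study", and "The used and unused amount of the IP will be assessed by the monitor by counting".
- Protocol 10.3: "Subjects will be requested to fill in a short diary in the multidose phase, on a daily basis, for confirming the product correct intake".

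The adverse event form in SAP 5.2.2.1 has a field for "Action taken with study device (categories: none, dose reduction temporarily, dose reduced, discontinued temporarily, discontinued"). The protocol has no text on dose reduction.

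**The concern.** The primary objective is to choose between 100 mg OD and 100 mg BID. The regimens differ by one after-lunch capsule a day, and SAP 5.2.1 compares the multidose pharmacokinetic parameters between arms with an unpaired t-test. A small difference could mean that the product adds little at the higher dose, or that the extra capsules were not taken. The planned outputs give no amount with which to tell these apart.

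The analysis sets are affected too. SAP 5.1.3 names non-compliance with study medication as a violation and decides major or minor case by case, with no numeric rule. The study is unblinded (SAP 2.6), and SAP 3.3 says that no data review is planned. In SAP 5.1.1 the same undefined item also serves as the at-least-one-dose test for the safety set. A subject who took capsules but was marked No at all three visits would fall out of that set, contrary to its definition in SAP 3.1.

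**Working it through.** The plan states no compliance rate, threshold or power, so there is no figure to reproduce. The check compares what is collected with what is reported, then works through the capsule arithmetic.

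**1. Collected against reported**

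| Source | What it could give | Use in the SAP |
|---|---|---|
| Capsule count (Protocol 9.7) | Total taken per subject | None |
| Daily diary (Protocol 10.3) | Intake by day | First and last intake dates (SAP 4.4); whether the diary was checked or returned (5.1.4) |
| Yes/no item at V3, V4, V5 | One answer per interval | Table 6, Listing 7, safety-set membership |
| Action-taken field on the AE form | Dose change linked to an AE | Text in Listings 18, 20 and 21 |
| Protocol violations | Non-compliance entry, free text | Table 8, Listing 6 |

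Treatment duration in SAP 4.4 is last date minus first date plus 1. It takes no account of missed doses, and no listed table reports it.

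**2. Prescribed amount** (28 days, 100 mg per capsule)

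- OD: 28 × 1 = 28 capsules, 2,800 mg
- BID: 28 × 2 = 56 capsules, 5,600 mg

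**3. What a count would show for a BID subject**

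Percent taken = capsules taken / 56. Mean daily dose = 100 × capsules taken / 28.

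| Missed | Taken | Percent | mg/day |
|---|---|---|---|
| 1 | 55 | 98.2 | 196.4 |
| 14 | 42 | 75.0 | 150.0 |
| 28 | 28 | 50.0 | 100.0 |

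The last row equals full OD dosing. If correct intake means no missed capsule (assumption), every row reads No in the affected interval.

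**4. Comparability of the yes/no item between arms**

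On the same assumption, with independent doses and per-capsule adherence p (assumed, 0.90 to 0.99), the chance of Yes at all three visits is p^28 for OD and p^56 for BID.

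| p | OD | BID |
|---|---|---|
| 0.99 | 75.5% | 57.0% |
| 0.98 | 56.8% | 32.3% |
| 0.95 | 23.8% | 5.7% |
| 0.90 | 5.2% | 0.3% |

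At p = 0.95, Yes at V3 or at V4 (7 days each) has probability 69.8% against 48.8%. At V5 (14 days) it is 48.8% against 23.8%. Equal adherence per capsule would look worse in the BID column of Table 6 only because twice as many capsules are at risk.

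**5. The dose contrast depends on both arms**

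The prescribed contrast is 200 − 100 = 100 mg/day. If only BID subjects miss 25% (assumed), it is 150 − 100 = 50. If both arms miss 25%, it is 150 − 75 = 75. The planned outputs would not show which applies.

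**The case against.** The strongest reply is that the plan is not blind to non-compliance. The diary is checked at the same visits at which the yes/no item is answered, so that item probably summarises the diary. SAP 4.4 also takes intake dates from the diary. Listing 7 gives the answers by subject and arm, violations have their own table and listing, and the AE listings print the action taken. This stands. A reader might infer that a BID subject on a reduced dose would be invisible, and the documents do not support that. What is missing is the amount, and AE listings do not capture capsules skipped for reasons unrelated to an adverse event.

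A reader might also infer that the form permits dose reduction. The field records an action and authorises none, and Protocol 11.1.5 leaves AE management to the investigator. The gap is that its categories have no matching protocol text.

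Nor do the documents support a forecast of how far the result would be diluted. Nothing in them says that lunch capsules are likelier to be missed. The 2.5 and 3.5 microg/ml levels are literature values for a well-absorbed supplement, and the protocol warns that levels depend on the formulation. It follows that 1.0 microg/ml is not this trial's expected difference.

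The count has limits of its own. It is an end-of-study total, and SAP 5.1.4 lists no CRF variable for it. Protocol 9.10 supplies two 30-capsule boxes with one box as reserve, so the number dispensed needs a definition. The 28 and 56 are nominal: SAP 4.4 takes diary Day 28 as last intake, while V5 falls on Day 28 with early-morning fasting sampling and product is retrieved there. If dosing runs from Day 1 and stops before that visit, the expected numbers are 27 and 54.

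Finally, the study is exploratory, the ITT comparison would not change and the per-protocol results are only supportive. That limits the consequence, but a descriptive comparison of two doses still needs the doses taken.

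**Conclusion.** The point holds as a reporting and derivation gap that should be closed. Multidose compliance is an undefined yes/no per visit interval, and no planned output quantifies intake in a trial whose arms differ only in capsules per day. If correct intake means no missed capsule, the item cannot separate 98.2% from 50.0% adherence in a BID subject, and its Yes rates are not comparable between arms. Those two statements rest on that reading, and the percentages in step 4 also rest on assumed adherence and independent doses. The absence of any amount rests on no assumption. No ITT estimate is wrong because of this. What suffers is the interpretation of the OD/BID contrast and the basis for per-protocol exclusion.

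**What to change.** In SAP 5.1.4, replace the empty derivation entry as follows:

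- Transfer the accountability counts to the database.
- For each subject over V2 to V5, derive capsules taken (dispensed, including any reserve box opened, minus returned), percent of prescribed capsules, and mean mg/day. Take the expected number from the subject's actual first and last dosing dates, nominally 28 for OD and 56 for BID.
- Use the diary for the breakdown by visit interval, since the count gives only a total.
- Report these by arm in Table 6 and by subject in Listing 7.
- Define the taken-correctly item and, before database lock, fix the percent compliance that counts as a major violation for the per-protocol set.
- Keep ITT as randomised.

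The sponsor should reconcile the dose-reduction categories on the AE form with the protocol, which has no corresponding text.

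The cost is SAP wording, a few derived variables and table rows, and entry of counts and diary data for 24 subjects. It adds no visit or blood sample.
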